Participants will complete 24-hour dietary recalls and collection of rectal biopsy, blood and urine samples, and possibly collection of stool, rectal swab, hair, nail and saliva samples at baseline, and at the end of treatment, and will complete study questionnaires at baseline, throughout the treatment, and at the conclusion of treatment. Questionnaire data to be collected include diet, medication use, health history, and other cancer risk factors. Biospecimens collected at baseline and at the end of intervention include a rectal biopsy sample, a first morning urine specimen, a blood sample (possibly fasting), stool, rectal swab, hair, nail and saliva. An additional collection of a blood sample, a urine sample, stool, rectal swab, and saliva will be done at the midpoint of the intervention phase. Medical records will be reviewed for hyperplastic polyp or/and adenoma pathology information at baseline. In addition to two baseline 24-hour dietary recall assessments, two 24-hour dietary recalls will be conducted during weeks 1 - 6, and two at weeks 7 - 12 of the trial. The research staff in the SRSR will also contact the participants to monitor for any adverse events and the study compliance, 12 times in total (4 times together with 24- hour dietary recalls). The duration of the study from recruitment through the end of the intervention is approximately 14 weeks including a 12-week intervention.

Throughout the course of the introductory and intervention phases, the participant will have multiple contacts with the study staff including both in-person and telephone contacts. Provided below are details related to each of these contacts and time frame of this study. Participants will be compensated \$250 -300 for participation at the end of the study depending upon the participant's provision of fasting blood collection.

Table A. Participant Study Protocol

	Baseline		Week of Intervention										
	-0	0	1	2	3	4	5	6	7	8	9	10	11
Introduction Letter	X												
Telephone Contact													
Questionnaire	X												
24 hr Dietary Recall(s)*	XX				XX					XX			
Monitoring/Compliance*					XXX					XXX			
In-person visit													
Questionnaires	X	X							X				X
Monitoring/Compliance*									X				X
Rectal Biopsy Sample	X												X
Rectal Swab	X												X
Blood Sample	X							X					X
Urine Sample	X							X					X
Stool Sample	X							X					X
Saliva Sample	X							X					X
Skin Swab Sample	X							X					X
Hair Sample	X												X

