Dietary Intake Assessment Protocol

We have collected a FFQ in the TCPS (IRB # 090235). In this study, we will perform two baseline 24-hour dietary recall assessments for each participant to update intake information during the introductory phase of the study prior to the supplementation of magnesium. The assessments will take place by telephone and will include one weekday and one weekend day where possible. The Ca/Mg intake ratio will be calculated from the 24-hour recalls to confirm the current ratio, to determine eligibility, and to determine the appropriate dose of magnesium supplementation in the treatment arm to reduce the ratio to < 2.6 or the number of placebo capsules in the placebo arm. They will also be used to verify the dietary Ca/Mg intake ratio, excluding any treatment magnesium, remains stable throughout the intervention period. Thus participants will also complete 4 additional 24-hr dietary assessments during the intervention phase; 2 times of diet recalls at week 1 - 6, and 2 times at week 7-12 throughout the course of the magnesium treatment.

Dietary intake will be measured using the 24-hour recall (24HR) assessment approach. The 24HR is the least biased method of dietary assessment during an intervention. Compared to a food record or food diary, the 24HR is less time consuming for the participant, and does not rely on their concentration and recording skills. The 24HR approach is interviewer based, and the interviewer is able to probe as needed. Therefore, dietary monitoring is not as reliant on the personality attributes of the study participant. Nutrient scores from multiple 24HRs are highly correlated with nutrient scores from a food record, and the total variance of nutrient scores from multiple 24HRs is smaller than the variance derived from food records.

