- Each 24HR requires about 30 minutes.
- Four additional 24-hr dietary assessments will be conducted during the intervention phase; 2 times of diet recalls at week 1 - 6, and 2 times at 7-12 throughout the course of the magnesium treatment.
- Nutrient scores are calculated from each 24HR (e.g., fat g/d, energy kcal/d, calcium mg/day, etc.) using the Nutritional Data System (University of Minnesota). Vitamin, mineral, fiber and other supplementation use are monitored by the 24HRs, and nutrients derived from supplementation are added to nutrients from dietary sources.

The procedures for completion of two baseline 24-hour recalls using a food-record assisted dietary recall approach (April, 2012)

It was very time-consuming to complete the two baseline 24-hour diet recalls by calling the participants twice at one weekday and at one weekend day, which might slow down the participant recruitment process. To speed up the participant recruitment, in April of 2012, we plan to use a new approach of food-record assisted 48-hour diet recall, utilizing the two-day food records to complete two 24 hour dietary recalls over one phone call interview. Based on the current 24-hour recall data we collected in our study, we found the weekday nutrient intakes are similar to those on the weekend day. Participants will be assigned to complete two-day food records of any one of the six combinations, Monday and Tuesday, Tuesday and Wednesday, Wednesday and Thursday, Thursday and Friday, Friday and Saturday, or Saturday and Sunday. The detailed procedures are described as follows.

- Participants will be told of the calls at initial contact and in informed consent document.
- Convenient windows of time to call participant are confirmed.
- Participants will receive a Food Amounts Booklet, two Food Record Forms, Food Record Instructions by mail (FOOD AMOUNT BOOKLET, FOOD RECORD FORMS, FOOD RECORD INSTRUCTIONS, Appendix C).
- Participants will complete two food records of any one of the six combinations of day of week, Sunday and Monday, Monday and Tuesday, Tuesday and Wednesday, Wednesday and Thursday, Thursday and Friday, Friday and Saturday, which will be randomly assigned to participants. The participants will record all the foods and drinks they have from the twelve midnight of the assigned day of week to the next twelve midnight. They will complete two food record forms in two consecutive days of the week. A separate form will be used for each day.

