- If individuals have had an acute or short-term illness in the past two days (48 hours), which substantially changed their usual diet, the two food records should be completed over the two days after their diet changes back to normal.

- The two baseline 24-hour dietary recall assessments for each participant will be made to obtain current intake information prior to the baseline treatment by one telephone interview. The phone call will be placed within a couple of days after participants complete their food records.
- A trained research member in the SRSR telephones the participant (Script for 48 Hour Dietary Recall_2012, Appendix C) and asks what they consumed the two days before they are called.
 - Working through each meal, snack, beverage, and supplement information is entered directly into a computer
 - The Nutritional Data System will calculate nutrient scores
- Each 24HR requires up to 30 minutes.
- Four additional 24-hr dietary assessments will be conducted during the intervention phase; using the record-assisted method, two times of diet recalls at week 1-6 and two times at week 7-12 throughout the course of the magnesium treatment.
- Nutrient scores are calculated from each 24HR (e.g., fat g/d, energy kcal/d, calcium mg/day, etc.) using the Nutritional Data System (University of Minnesota). Vitamin, mineral, fiber and other supplementation use are monitored by the 24HRs, and nutrients derived from supplementation are added to nutrients from dietary sources.
- If missed, the phone call will be placed and completed immediately on the next two days.

Prior to enrollment, two baseline 24 hour dietary recalls are performed to estimate participants' current diet intake information for determining participants' eligibility and for calculating the dosage of magnesium/placebo supplementation. The time interval window between 24 hour recalls and the first clinical visit should be within approximately 3 months. Otherwise the two baseline 24 hour diet recalls should be conducted again.

D. Baseline Interview

Baseline Telephone Interview

The research staff in the Survey Research Shared Resource (SRSR) will administer a study questionnaire (Appendix D) at baseline. Questionnaire data to be collected include diet, medication use, health history, physical activity and other cancer risk factors.

E. Randomization and Intervention

Randomization Protocols

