The goal of this study is to evaluate the main effect on carcinogenesis related biomarkers, inflammatory biomarkers and magnesium status by reducing the dietary Ca/Mg intake ratio to under 2.6 by magnesium supplementation on carcinogenesis related biomarkers, inflammatory biomarkers and magnesium status and to estimate the potential interaction between magnesium treatment and the Thr1482Ile polymorphism (G→A) of the *TRPM7* gene. The study will enroll 288 participants with colorectal hyperplastic polyp or/and adenoma, polyps free but being at high risk of colorectal polyps or cancer, 152 of whom have the GG genotype and 136 of whom have GA/AA genotype. These participants will be randomized to either treatment or placebo using a double-blind two-factorial (Ca/Mg intake ratio and genotype) design so that each treatment/placebo arm will contain 60 participants with the GG genotype and 60 participants with at least one A allele. Based on the participant's Ca/Mg intake ratio (obtained from the two 24-hour recalls), he or she will be assigned to a dose that will reduce the Ca/Mg intake ratio to around 2.3 (less than 2.6 but no less than 2.0). The dose of magnesium supplementation is personalized based on the current intake ratio. The duration of the study from recruitment through the end of the intervention is approximately 14 weeks including a 12-week intervention. (See attached Figure E2)

The trial will be double-blind: neither participants nor research staff who interacts with the participants or their samples will be aware of the treatment assignments. The treatment period will last for 12 weeks.

Procedures:

1. Intervention layout

- Based on the participant's Ca/Mg intake ratio (obtained from the two 24-hour recalls), the participant will be assigned to a dose that will reduce the Ca/Mg intake ratio to around 2.3 (less than 2.6 but no less than 2.0). Each dose will correspond to one or multiple capsules from three different sizes of magnesium supplementation or placebo.
- Presented in Table E2 is the detailed treatment dosage based on baseline calcium/magnesium ratio and calcium intake level as well as resulting calcium/magnesium ratio after supplementation. Treatment or placebo capsules will be discarded if they are not used within 6-months.

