7.0 Risks

Physical Risks

Adverse events associated with oral magnesium supplementation include nausea, cramping abdominal pain, and diarrhea. These effects are caused by the osmotic action of unabsorbed magnesium salts. The magnesium supplement that has been selected for this study is magnesium glycinate. This magnesium salt readily dissolves within the intestinal tract and is less likely to cause gastrointestinal symptoms when compared to other forms of magnesium supplementation. Participants will be generally healthy and able to take all supplementation by mouth. Magnesium supplementation is not a prescribed medication, instead, it is considered a dietary supplement.

Magnesium toxicity should not occur in normal healthy subjects enrolled in this intervention trial. Excess oral intake of magnesium through dietary sources and supplement use is readily excreted by the kidneys. Magnesium supplements should be avoided in individuals with severe renal insufficiency as elevated blood levels of magnesium and toxicity can occur in these individuals. Subjects with renal insufficiency will be excluded from this investigation. Should a study subject developed acute renal insufficiency the development of magnesium toxicity is possible. However, if this were to occur it is much more likely that the study subject will present with symptoms of renal insufficiency rather than magnesium toxicity. Having said this, the oral intake of 30 g of magnesium daily can lead to metabolic alkalosis and hypokalemia. A single dose of over 400 g of magnesium can result in paralytic ileus and cardiorespiratory arrest. It is highly unlikely that any of these events will occur during the course of the study as the dosage form of the supplement is far below this amount.

Magnesium salts, especially those in antacids, may decrease the bioavailability and absorption of digoxin, chlordiazepoxide, and several antibiotics, including tetracycline, aminoquinolone and nitrofurantoin. It may also increase the absorption of dicumarol. Subjects who are on these medications will be instructed to take the study supplement at least two hours before or after one of these medications. Individuals currently receiving dicumarol will be excluded from participation in the study.

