Standard graphing and screening techniques will be used to detect outliers and to ensure data accuracy. Distributions of continuous outcomes will be assessed for normality. If normality is violated, proper data transformation will be applied or non-parametric analysis methods will be considered. Summary statistics for both continuous (mean \pm standard deviation) and categorical variables (count and percent) will be provided by randomization groups to describe the study sample. Specific inferences on effects of interest will be made by reporting a point estimate along with a 95% confidence interval and the p value. Hypotheses will be tested at the level of $\alpha=0.05$. This data analysis plan will be carried out using statistical software SAS® (Cary, North Carolina) or statistical analysis package R (R Development Core Team, 2008). These basic statistical rules will be applied to all study aims.

Two-way ANOVA or ANCOVA analyses will be conducted to analyze the primary and secondary endpoints with intervention and genotype in the model (ANOVA) or other potential confounders including polyp type, size, and location for primary hyperplastic polyp or/and adenoma as well as body mass index, age, total energy intake, and intakes of other nutrients (average of six 24-hour recalls) in the model (ANOCOVA). Overall intervention effect and genotype effect and their interactions will be tested.

Univariate analyses will be conducted for these ten primary and secondary end points (continuous variables) in relationship to magnesium treatment and placebo using between-group t-test or non-parametric tests within genotype groups. The difference in the study endpoints (primary+secondary) between magnesium supplement and placebo will be estimated for the genotype groups (GG, GA, AA and GA and AA combined) along with their 95%

confidence intervals. The interaction between the genotype and intervention will be estimated as the difference of the within-genotype magnesium supplement versus placebo differences.

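### The optional ANCOVA adjusts for nutrient intake averaged over six recalls, four of them on treatment, so its treatment effect is biased if magnesium shifts recorded intake and intake relates to the endpoint

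*Combined protocol and SAP*

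**What the plan says.** Section 9.0 (Data analysis plan) and section 6.0 I (Data Analysis, Procedures) carry the same text. The endpoints are to be analysed by two-way ANOVA, with intervention and genotype in the model, or by ANCOVA with further potential confounders added. Among those confounders are "total energy intake, and intakes of other nutrients (average of six 24-hour recalls) in the model (ANOCOVA"). Neither model is named as primary. The wording leaves open whether the parenthesis also covers total energy.

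Section 6.0 shows what the six recalls are:

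- Baseline: "Prior to enrollment, two baseline 24 hour dietary recalls are performed to estimate" current intake, for eligibility and dose calculation (6.0 C).
- On treatment: "two 24-hour dietary recalls will be conducted during weeks 1 - 6, and two at weeks 7 - 12 of the trial" (6.0 A). Section 6.0 C agrees: "participants will also complete 4 additional 24-hr dietary assessments during the intervention phase". Both recall procedures in 6.0 C also give four, the recall-only one ("Four additional 24-hr dietary assessments will be conducted during the intervention phase; 2 times of diet recalls at week 1 - 6") and the record-assisted one ("Four additional 24-hr dietary assessments will be conducted during the intervention phase; using the record-assisted method").

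The plan does not restrict the covariate to the baseline recalls, and it gives no rationale for adjusting for intake on treatment.

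**The concern.** Randomisation balances what exists before it. Intake recorded afterwards cannot confound a randomised contrast. It can differ between arms only by chance or because treatment changed it. In the second case, holding it fixed changes the treatment effect being estimated and may remove or add part of it.

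A route is conceivable here. Section 7.0 states: "Adverse events associated with oral magnesium supplementation include nausea, cramping abdominal pain, and diarrhea". Such symptoms could alter what participants eat and report. Because the plan offers the ANCOVA for every primary and secondary endpoint, an adjusted result exposed to this bias could be the one reported for any of them.

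**Working it through.** **Share measured after randomisation.** 4 of 6 recalls = 67%.

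**Scale, from the power analysis in 9.0.** This uses erythrocyte magnesium, which the data analysis plan does not list as an endpoint, so it serves only as a scale. Inputs: 60 per cell (120 per arm), SD 0.83, treated means 5.25 in both genotype groups, untreated means 5.25 (GG) and 4.49 (GA/AA).

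- Main effect = (0 + 0.76)/2 = 0.38 mg/dL.
- Unadjusted SE = 0.83 × √(2/120) = 0.107.
- Power = Φ(0.38/0.107 − 1.96) = 94%, as stated. With SD 1.16 it is 71.5% (F) or 71.8% (normal), against the stated 71%.

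The plan's own figures therefore reproduce. The point concerns the definition of the covariate only.

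**Bias formula.** Let b be the slope of the endpoint on usual intake (per between-person SD), d the shift that treatment causes in on-treatment recorded intake (in the same SDs), and λ the within-person to between-person variance ratio of a single recall. The reliability of a six-recall mean is r = 1/(1 + λ/6). The adjusted main effect equals the true effect minus b × r × (4/6) × d. It is too small if b and d push in the same direction as the effect, and too large by the same amount if the sign of d reverses. If b = 0 or d = 0 the bias is zero.

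**Assumed values, not in the documents.** λ = 1, so r = 0.857; b = 0.1 or 0.3 mg/dL per SD (0.12 or 0.36 endpoint SD per SD, dividing by 0.83); |d| = 0, 0.25 or 0.5. Power and false-positive rates are from a simulation with 60 per cell and 6,000 replicates.

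| b | \|d\| | Bias (mg/dL) | Adjusted effect, d positive / negative | Power, d positive | False-positive rate, no true effect |
|---|---|---|---|---|---|
| 0.1 | 0 | 0 | 0.38 | 95% | 5% |
| 0.1 | 0.25 | 0.014 | 0.37 / 0.39 | 93% | 5-6% |
| 0.1 | 0.5 | 0.029 | 0.35 / 0.41 | 90% | 5-6% |
| 0.3 | 0 | 0 | 0.38 | 96% | 5% |
| 0.3 | 0.25 | 0.043 | 0.34 / 0.42 | 91% | 7% |
| 0.3 | 0.5 | 0.086 | 0.29 / 0.47 | 82% | 13% |

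The largest entry is 0.3 × 0.857 × 0.667 × 0.5 = 0.086, which is 23% of 0.38. With λ = 2 or λ = 0 it becomes 0.075 or 0.100. In endpoint SD units, which carry over to the mucosal markers, the bias at |d| = 0.5 is 0.029/0.83 = 0.03 to 0.086/0.83 = 0.10.

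**Both signs.** A separate simulation (2,000 replicates, endpoint-intake correlation 0.3, so b = 0.3 × 0.83 = 0.249) gave 0.309 at d = +0.5 and 0.451 at d = −0.5, with power 84% and 99%. The false-positive rate was 10% and 11%. The formula predicts a bias of 0.071 either way. The higher power under the negative shift reflects an overstated effect, so it is no gain.

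**Interaction.** This is biased only if the shift differs by genotype. If A-allele carriers alone shift by 0.5 SD, 0.76 becomes 0.731 (b = 0.1) or 0.674 (b = 0.3).

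**Baseline-only covariate.** With the two baseline recalls, the estimate is 0.38 and the false-positive rate about 5% in these settings. In the worst case tabulated above, power is 96%.

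**The case against.** The strongest reply is that a material shift is unlikely. The trial is double-blind: "neither participants nor research staff who interacts with the participants or their samples will be aware of the treatment assignments". Section 6.0 E says the salt was chosen to avoid a laxative effect, 7.0 says it is less likely than other forms to cause gastrointestinal symptoms, and 6.0 G cites good tolerability. Diarrhea and cramping are to be managed. Section 6.0 C delays a recall when acute illness has substantially changed the diet, although that rule sits under the baseline procedures and would not cover persistent symptoms. All this stands as a reason to expect a small shift. It does not exclude one, since blinding does not block a physiological effect on eating.

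The second reply is that unaffected analyses already exist. The unadjusted ANOVA tests treatment, genotype and their interaction, and the within-genotype comparisons estimate the treatment differences directly. This stands in full and limits the reach of the point to one optional model.

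The third is that six recalls measure diet better than two, and that genotype, which is not randomised, may need dietary adjustment. Both are true, but the precision gained is very small (see the cost of the change), and baseline recalls can serve the genotype adjustment too.

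A reader might infer that the trial's treatment effect is biased, or that power will fall to 82%. The documents support neither. They give no slope and no shift, and the 82% needs the steeper assumed slope, the larger assumed shift and one particular sign. Reduced intake from nausea or diarrhea, combined with a positive slope, would instead overstate the effect.

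**Conclusion.** The point holds in a limited form and should be corrected. The ANCOVA as defined conditions the randomised contrast on a covariate that is two-thirds post-randomisation. Bias requires that treatment shifts recorded intake and that intake relates to the endpoint. A chance difference in intake between arms is not bias, so seeing one in the data would not by itself show that the adjusted estimate is wrong.

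The definition of the covariate is certain from the text. The size and direction of any bias are not known. The illustrative range is 0.03 to 0.10 endpoint SD, either sign, and it rests on an assumed 0.5 SD shift, slopes of 0.12 to 0.36 SD per SD, and equal within-person and between-person variance. At the lower slope the false-positive rate hardly moves.

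**What to change.** In sections 9.0 and 6.0 I, define every dietary covariate in the ANCOVA, including total energy, as the mean of the two baseline 24-hour recalls instead of the six-recall mean. If a model using the on-treatment recalls is wanted, keep it as a labelled exploratory or mediation analysis.

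This changes wording only, because the baseline recalls are already required for eligibility and dosing. The cost is a slightly noisier measure of diet. With SE = 2 × √(0.83² − b² × r_k)/√240, and r_6 = 0.857 and r_2 = 0.667 at λ = 1:

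- b = 0.1: 0.1065 with six recalls, 0.1066 with two (0.1% larger).
- b = 0.3: 0.1010 with six, 0.1024 with two (1.4% larger).
- b = 0.3 with λ = 2: 1.8% larger.

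The formula treats recalls as independent and unselected. Because baseline calcium intake and the Ca/Mg ratio also determine eligibility, and record-assisted days are consecutive, the cost for calcium-related covariates may be somewhat higher, though still small.
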